11 STUDY DRUG AND OTHER MEDICATIONS

11.1 Exposure to Study Drug and Study Treatment Compliance

Summaries of study drug exposure and compliance will be summarized overall and separately for those taken during Placebo-Controlled Treatment Period and the Open-Label Treatment Periods of the study and overall for the Safety Analysis Set and the PP Analysis Set. The source for study drug dosing and compliance is drug accountability.

The summaries will include the total number of doses taken, mean daily dose (mg/day), duration (days) of exposure, and study drug compliance by treatment group.

The drug accountability information, including number of tablets dispensed, number of tablets returned, number of tablets lost or destroyed, and reasons/comments for incomplete or missed doses, along with all summarized variables, will be listed in subject listings. Subject dosing diary information, along with diary compliance, will also be listed in a separate listing.

11.2 Glucocorticoid Therapy

Changes in GC therapy will be summarized overall and separately for those taken during each Treatment Period (Placebo-Controlled, Open-Label) of the study and overall. The source of GC regimen change is the concomitant medication eCRF.

The following items will be summarized, proportion of subjects with a stress dosing event, number of unique stress dosing events, duration of stress dosing events. The source of GC stress dosing is the GC daily diary. All the above information will be included in a subject listing.

11.3 Prior and Concomitant Medications

Prior and concomitant medications, other than glucocorticoids, will be summarized using WHO DD ATC class and preferred name. The summary results will be presented by Treatment Period (Placebo-Controlled, Open-Label). Prior medications will be summarized by randomized treatment group. Concomitant medications will be summarized by actual dose taken concomitantly during each treatment period.

These summaries will present the number and percentage of subjects using each medication. Subjects may have more than one medication within an ATC class and preferred name. At each summary level subjects are counted once if they reported one or more medications at that level. Each summary will be ordered by descending frequency of incidence of ATC class and preferred name within each ATC class.

All medications will be provided in a subject listing including, but not limited to: Start date/end date/ongoing, medication name, ATC class and preferred name, indication, dose, unit, form, frequency, and route.

11.3.1 Prohibited Concomitant Medications

Any use of prohibited and cautionary concomitant medications during the study will be identified. A summary table of prohibited concomitant medications will be presented similar to that of concomitant medications. A separate subject listing of prohibited and cautionary concomitant medications will be provided.

12 EFFICACY ANALYSES

12.1 Primary Efficacy Analyses

The Primary Analysis is planned after all subjects have completed the Week 24 visit at the end of the Placebo-Controlled Period of the study. The data from Baseline through Week 24 will be hard-locked prior to the Primary Analysis.

During this first 24-week of double-blind, placebo-controlled treatment period, the scheduled visits included in this treatment period include Day 1, Week 3, Week 6, Week 12, Week 18, and Week 24.

Efficacy analyses will compare the tildacerfont dose group to the placebo group with respect to

- The Primary Efficacy Endpoint (see [Table 5](#))
- Secondary Efficacy Endpoints (see [Table 5](#))
- and Exploratory Efficacy Endpoints (see [Table 5](#))

These efficacy analyses will be performed using the ITT Analysis Set. The PP and mITT Analysis Sets will be used as supplemental for the primary and Secondary Efficacy Endpoint analyses. The Primary Efficacy Endpoint, select Secondary Efficacy Endpoints and select Exploratory Efficacy Endpoints (as outlined in [Table 5](#)) will be analyzed at the Primary Analysis.

12.2 Final Efficacy Analyses

The Final Analysis will occur after the last subject has completed the Week 76 visit or if the study is discontinued by the Sponsor. The data from Week 24 through Week 76 + follow-up will be hard-locked prior to the Final Analysis.

The scheduled visits included in this treatment period include Day 1, Week 3, Week 6, Week 12, Week 18, Week 24, Week 32, Week 40, Week 52, Week 64, Week 76 and Follow-up visits.

Exploratory Efficacy Endpoints along with select Secondary Efficacy Endpoints (as outlined in [Table 5](#)) will be analyzed at the Final Analysis.

12.3 Primary Efficacy Endpoint Analysis

The primary objective of the study is to evaluate GC dosage change in HCe in subjects with CAH over the 24-week, double blind, Placebo-Controlled Treatment Period.

12.3.1 Definition of Primary Efficacy Endpoint Estimand

The primary “treatment policy” estimand is the absolute change from baseline in GC dose in HCe at Week 24 post randomization. In the original study protocol, the primary endpoint was defined in a binary fashion as the proportion of subjects with at least a 5 mg/day HCe reduction from baseline in GC dose and $A4 \leq ULN$ at Week 24. Consistent with the emerging analysis of competitor trial data, and also realizing the loss of information and power associated the reduction of continuous data to a simple binary form, the primary endpoint definition was changed from binary to a continuous change from baseline and, hence, the associated use of MMRM analysis below. Nevertheless, binary evaluation of the primary endpoint is still retained in the SAP in the form of supportive secondary analyses.

Population: The analysis population is the ITT analysis set, including all classic CAH subjects who were randomized into the study

Variable: The analysis variable is the absolute change from baseline to Week 24 in GC dose in HCe.

Intercurrent events: For the Primary Efficacy Endpoint analysis, intercurrent events such as changes in GC type or lack of treatment compliance or GC compliance, treatment interruption or discontinuation, use of prohibited medications will be ignored.

12.3.2 Primary Endpoint Statistical Hypotheses

For the Primary Efficacy Endpoint, the null hypothesis is that there is no difference in the mean change from baseline to Week 24 in GC dose in HCe. The alternative hypothesis will be that there is a difference between the treatment groups.

$$H_0: \mu_{200 \text{ mg QD tildacerfont}} - \mu_{placebo} = 0$$
$$H_A: \mu_{200 \text{ mg QD tildacerfont}} - \mu_{placebo} \neq 0$$

12.3.3 Statistical Modeling and Testing

An MMRM model will be used to analyze the Primary Efficacy Endpoint. The model will comprise the change from baseline as the dependent variable; randomized treatment group (0: placebo, 1: tildacerfont), visit (Weeks 3, 6, 12, 18 and 24), randomized treatment by visit interaction as fixed effects; baseline value as a continuous covariate; within subject error will be modelled using an unstructured covariance matrix; sex (0: male, 1: female), baseline GC type (0: short-acting, 1: intermediate-acting or combination) and CAH Type (0 =simple virilizing, 1=salt-wasting) will also be included as fixed effects. The estimation method will be restricted maximum likelihood (REML). The principal treatment effect of interest is at 24 weeks for which the associated LSmeans, difference in LSmeans, CI and 2-sided p-value will be extracted from the model; in addition, the same will be extracted for each earlier visit.

In the event the MMRM model with an unstructured covariance structure does not converge, the following covariance structures will be used as substitution in the order below. Each subsequent covariance structure will be used only if each previous covariance structure was used and the model did not converge:

- a) Toeplitz covariance structure (assuming measurements from samples taken closer together in time are more highly correlated than those from samples taken farther apart)

- b) First order of auto-regressive [AR(1)] covariance structure (assuming measurements from samples taken closer together in time are more highly correlated than those from samples taken farther apart)
- c) Compound symmetry covariance structure (assuming equal correlation for measurements from a subject, regardless of how far apart in time when they were taken)

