6.3 Measures to Minimize Bias: Randomization and Blinding

At the beginning of the Placebo-Controlled Treatment Period, subjects will be centrally randomized in a 1:1 ratio to receive placebo or tildacerfont at 200 mg QD using a randomization and trial supply management (RTSM) system. Randomization will be stratified by sex and baseline GC dose level (<40 mg/day and ≥40 mg/day in HCe).

Emergency unblinding to a subject's treatment assignment should only occur when knowledge of the treatment assignment is necessary for immediate medical management of the subject. If emergency unblinding is required, the Investigator may use the code provided at the site initiation visit to access the subject's treatment assignment details via the RTSM system.

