4.1 Randomization and Blinding

Subjects will be centrally randomized in a 1:1 ratio to receive tildacerfont at 200 mg QD or matching placebo using a randomization and trial supply management (RTSM) system. Randomization will be stratified by sex (male and female) and baseline GC dose level (< 40 mg/day and \geq 40 mg/day in HCe). Investigators, subjects, and the Sponsor will be blinded to assigned study drug for the duration of the Placebo-Controlled Treatment Period.

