9 STATISTICAL AND ANALYSIS ISSUES

9.1 Adjustments for Covariates

The categorical, randomization stratification variables sex (0 = male, 1 = female) and baseline HCe group (<40 mg/day and \geq 40 mg/day) will be used in all efficacy analyses. Additional categorical covariates may include baseline daily GC type (0 = short-acting, 1 = intermediate acting or combination) and CAH Type (0 =simple virilizing, 1=salt-wasting). Baseline daily GC dose in HCe or BSA adjusted dose may also be included as a continuous covariate. The baseline value of continuous efficacy endpoints will be included as a continuous covariate in statistical models, such mixed model repeated measures (MMRM), analysis of covariance (ANCOVA), or logistic regression.

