12.6.1.2 Subgroup Analyses

Subgroup analyses to Exploratory Efficacy Endpoints 3.1, 3.3, 3.4 and 3.8 to 3.15 will be performed as per [Section 12.5.2](#).

12.6.2 Analysis for Change and Percent Change from Baseline at Week 52 Exploratory Efficacy Endpoints 3.9, 3.11, 3.13, 3.15 and 3.16

An ANCOVA model will be used to analyses Exploratory Endpoints 3.9, 3.11, 3.13, 3.15 and 3.16. The absolute or change or percent change from baseline (placebo-controlled baseline; see section 8.3.9) to 52 weeks will be the dependent variable. The ANCOVA model will include terms for treatment group (0: placebo, 1: tildacerfont); the randomization strata: sex (0: male, 1: female) and baseline GC dose (in HCe, 0: < 40 mg/day, 1: \geq 40 mg/day); and baseline GC type (0: short-acting, 1: intermediate-acting or combination) as categorical explanatory variables. The difference in LSmeans between randomised treatment groups at Week 52 along with the associated CI and 2 sided p-value will be extracted.

Further, a paired t-test will be used to compare the change from tildacerfont-baseline to 52 weeks on treatment with tildacerfont.

In terms of descriptive statistics, for each type of analysis, the change from baseline will be reported by treatment group for the reported value and change from baseline value, and percent change from baseline value (if applicable) will also be presented.

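### SAP 9.1 requires both randomisation strata and the endpoint's baseline in the efficacy models, but the Week 52 ANCOVA lists no endpoint baseline and the primary MMRM lists no <40/≥40 mg stratum

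*SAP*

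**What the plan says.** Protocol 6.3 states: "Randomization will be stratified by sex and baseline GC dose level", with the cut at 40 mg/day HCe. SAP 4.1 repeats it.

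SAP 9.1 sets two general rules. On the strata: "The categorical, randomization stratification variables sex (0 = male, 1 = female) and baseline HCe group" (<40 and ≥40 mg/day) "will be used in all efficacy analyses". On baselines: "The baseline value of continuous efficacy endpoints will be included as a continuous covariate in statistical models", with MMRM and ANCOVA named among the examples. Continuous baseline GC dose appears in 9.1 only as an optional further covariate, not as a substitute for the dose group.

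The model sections then give their own lists:

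- **12.3.3, primary MMRM:** treatment, visit, their interaction, "baseline value as a continuous covariate", sex, "baseline GC type (0: short-acting, 1: intermediate-acting or combination) and CAH Type". The dose group is not listed.
- **12.3.3.1, imputation for the primary endpoint:** baseline GC dose appears as a continuous value. The dose group does not.
- **12.6.1, Week 24 exploratory endpoints (3.1, 3.3, 3.4, 3.8 to 3.15):** the 12.3.3 specification is reused.
- **12.6.2, Week 52 endpoints (3.9, 3.11, 3.13, 3.15, 3.16):** "The ANCOVA model will include terms for treatment group", followed by both strata and baseline GC type. The outcome is the change or percent change from the randomisation baseline. The endpoint's baseline value is not listed.

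The other regression models written out in full (12.5.1.1 secondary logistic, 12.6.4 cumulative dose, 12.6.5.3 adrenal biomarkers) name both strata, and the secondary imputation model in 12.5.1.2 names the dose group.

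**The concern.** Two different primary models can be read from one SAP: with the dose group (9.1) or without it (12.3.3). The clause in SAP Section 3 that lets the SAP prevail settles differences between SAP and protocol, not differences inside the SAP. Section 14, on changes from the protocol-specified analysis, is still a placeholder. The primary model should be unique before unblinding even if the alternatives give nearly the same answer.

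At Week 52 the stake is precision. A model for change that holds only categorical terms is an analysis of variance on change scores, whatever it is called, and it gives up the gain from adjusting for the endpoint's baseline.

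A third effect is less visible. In 12.3.3 the baseline covariate is baseline GC dose. When 12.6.1 carries that specification over to HOMA-IR, SF-36, BMI, waist circumference and body composition, the baseline covariate becomes that endpoint's own baseline. A stratification factor, baseline GC dose, is then absent from those models in any form.

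**Working it through.** **1. The plan's own figure.** SAP Section 6 gives at least 90% power for N=40 per group, difference 5 mg/day, SD 6.9, two-sided alpha 0.05. The standard error is 6.9 × √(2/40) = 1.543. Then 5/1.543 − 1.96 = 1.28, so power is 0.900 (0.893 with the t distribution). The figure reproduces to within a point. It is an unadjusted two-mean calculation, so none of the changes discussed here alters it.

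**2. Week 52: effect of adding the endpoint's baseline.** Let σ² be the variance of the endpoint, equal at baseline and Week 52, and ρ the correlation between the two.

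- Variance of the change score: 2σ²(1−ρ)
- Residual variance with baseline as a covariate: σ²(1−ρ²)
- Ratio: (1−ρ²) / [2(1−ρ)] = (1+ρ)/2

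The documents give no ρ, so a range is assumed:

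| ρ (assumed) | (1+ρ)/2 | Variance cut by adding baseline | Inflation without it, 2/(1+ρ) | Equivalent share of 90 subjects |
|---|---|---|---|---|
| 0.5 | 0.75 | 25% | 1.33 | 67.5 |
| 0.7 | 0.85 | 15% | 1.18 | 76.5 |
| 0.9 | 0.95 | 5% | 1.05 | 85.5 |

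The last column is 90 × (1+ρ)/2, taking the planned 90 subjects for illustration.

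The formula applies directly to absolute change: waist circumference (3.13), body composition (3.15) and BMD (3.16). It does not apply directly to percent change in BMI (3.11). SF-36 (3.9) has no scheduled Week 52 assessment: Protocol 1.3.4 and SAP 4.3.1.6 place it at Day 1, Week 24 and Week 76 within the Treatment Period. No gain can be claimed there.

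**3. Primary endpoint: effect of adding the dose group to a model that already holds continuous baseline dose.** This was simulated as a single-visit ANCOVA with 1:1 randomisation stratified by sex and dose group, n=80 and residual SD 6.9. There were 8,000 runs per setting. Assumed, because the documents do not give them: baseline dose distributed as 30 + 30 × Beta(1,2) mg, a slope of −0.2 mg change per mg of baseline, and a possible extra step at 40 mg.

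| Step at 40 mg (assumed) | Mean SE, without → with group | Power at 5 mg/day, without → with group |
|---|---|---|
| 0 | 1.542 → 1.550 (+0.5%) | 0.887 → 0.884 |
| 3 mg | 1.551 → 1.547 (−0.3%) | 0.888 → 0.886 |
| 6 mg | 1.581 → 1.547 (−2.2%) | 0.884 → 0.897 |

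With no treatment effect, the rejection rate was 0.050 to 0.054 in all six cases. Power moved by 0.2 to 0.4 points downwards without a large step, and by 1.3 points upwards with a 6 mg step.

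**The case against.** The best counter-argument concerns the primary model. Baseline GC dose is there as a continuous covariate and the stratum is a two-level cut of it, so together with sex both stratification factors are already adjusted for. That stands. The simulation supports it: with a linear dose effect the extra term slightly raises the standard error, and a gain needs a sizeable step at exactly 40 mg, for which the documents offer no evidence. The protocol does not require the stratum in the MMRM either. The reference to randomisation strata in Protocol 9.4.2 is attached to an exact test through logistic regression, a method for binary outcomes. The synopsis gives GC dose endpoints an ANCOVA with baseline dose and treatment only. The synopsis does name the dose group as an imputation factor, but the SAP governs there, and 12.3.3.1 carries baseline dose in continuous form.

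For Week 52 it can be said that 9.1 supplies the missing covariate, since 12.6.2 does not call its list exhaustive. Also, endpoints 3.9, 3.11, 3.13 and 3.15 fall inside the range in 12.6.1, which inherits a baseline term. This makes it an omission to be clarified rather than an outright contradiction. It does not remove the problem: the precision is lost if the model is programmed from 12.6.2 as listed, those four endpoints have two candidate models, and BMD (3.16) has 12.6.2 as its only specific model section.

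The redundancy argument does not carry over to the non-GC endpoints in 12.6.1, where continuous GC dose is not in the model.

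**Conclusion.** The inconsistency is real and its consequences are small. At Week 52, listing the endpoint's baseline would cut the variance by 5% to 25% for absolute-change endpoints. This assumes equal variances and ρ between 0.9 and 0.5. It concerns exploratory endpoints outside the multiplicity procedure in SAP 9.6, at a time when both arms receive tildacerfont. For the primary endpoint, the two candidate models differ by about 1 point of power under the simulated assumptions, with type I error near 5% for both. The issue there is having one pre-specified model, not validity.

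A reader might infer that the primary analysis ignores a stratification factor, or that its type I error or power is compromised. The documents do not support that, because continuous baseline dose is in the model. A reader might also infer that every Week 52 endpoint loses up to a quarter of its precision. That does not follow either: ρ is assumed, percent change in BMI is outside the formula, and SF-36 has no scheduled Week 52 data.

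**What to change.** 1. **12.6.2:** add the endpoint's own baseline as a continuous covariate, using the same randomisation baseline from which the change is calculated. This is the main change.
2. **9.1 and 12.3.3:** make them agree. Either add the RTSM dose group (<40/≥40 mg/day) to the primary MMRM and to the imputation models in 12.3.3.1, or state in 9.1 that continuous baseline GC dose replaces the group for the primary endpoint. Either is acceptable; the choice should be made before unblinding.
3. **12.6.1:** under either option, add the dose group wherever the 12.3.3 specification is reused for HOMA-IR, SF-36, BMI, waist circumference and body composition.

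The cost is a few lines of model text and one degree of freedom per model. All the variables are already collected or used at randomisation.

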4.1.2.3 Telephone Contacts

Sites will make scheduled telephone contacts during the Glucocorticoid Conversion Period at Weeks -11 and -6 (and -5, if applicable) and during the Treatment Period at Weeks 27 and 46 to record any AEs and concomitant medications.

After receiving A4 results from the Day 1 (dose reduction only) and Week 6, 12, 18, 24, 32, 40, 52, and 64 study visits, or during the optional Open-Label Extension Period, sites will make telephone contacts to subjects who are eligible for a GC dose adjustment. Sites will contact these subjects within 2 weeks after each applicable study visit. The site will direct the subject to adjust his/her GC dose at that time if the subject has not experienced any change in clinical status since the previous study visit. If no GC dose adjustment is warranted based on the A4 level, the site does not need to contact the subject. If a subject's GC dose is adjusted, the site will telephone the subject again 7 days after the GC dose adjustment to assess for the occurrence of AEs and the initiation of new concomitant medications.

Subjects should be instructed to telephone sites if they have any concerns about their health.

PRN telephone contacts initiated by sites and telephone contacts initiated by subjects should be captured in the EDC system as "unscheduled" telephone contacts.

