4.3.1 Efficacy Assessments

4.3.1.1 Hormone Assessments

All blood samples for hormones and androgens will be collected at approximately 8 AM (7- 9 am window) prior to administration of a subject’s morning GC dose. A4, 17-hydroxyprogesterone (17-OHP), adrenocorticotropic hormone (ACTH), and testosterone will be measured. Hormone assessments will be collected at all study visits except for Week 3 (safety laboratory assessments only).

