6 SAMPLE SIZE AND POWER

The original sample size calculation was based the binary endpoint of percent of subjects with a 5 mg/day HCe reduction from baseline in GC dose at Week 24 with $A4 \leq \text{ULN}$. Assuming a

placebo group response of 30%, N = 45 subjects per group would provide at least 90% power to detect a between group relative difference of 33% at the 0.05 two-sided type I error rate.

Additionally, it was computed that a sample size of N=45 subjects per group would provide at least 90% power to detect a mean change in daily GC dose from baseline and placebo of 7.25 mg/day in HCe, assuming a standard deviation (SD) of 10.5 mg/day HCe and the two-sided type I error is 0.05. Examination of group blinded data, provides a conservative SD estimate of 6.9 mg/day. On this basis, a sample size of N=40 subjects per group provides at least 90% power to detect a mean change in daily GC dose from baseline and placebo of 5 mg/day in HCe with a two-sided type I error of 0.05.

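### If the unstructured primary MMRM does not converge, the named fallback covariance structures assume one variance for all visits and would make the Week 24 standard error too small

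*SAP*

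**What the plan says.** SAP 12.3.3 models change from baseline in GC dose at Weeks 3, 6, 12, 18 and 24, with treatment-by-visit terms and an unstructured within-subject covariance. It continues: "In the event the MMRM model with an unstructured covariance structure does not converge, the following covariance structures will be used as substitution". The list is Toeplitz, then AR(1), then compound symmetry. Each is described only by its correlation pattern. No heterogeneous-variance version, sandwich standard error or degrees-of-freedom method is named. Under SAP 12.3.3.1 the same model is fitted to every imputed dataset.

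The dosing rules that generate the outcome are elsewhere:

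- Protocol 4.1.2.3 ties adjustment calls to A4 results: "After receiving A4 results from the Day 1 (dose reduction only) and Week 6, 12, 18, 24, 32, 40, 52, and 64 study visits". Calls are made within 2 weeks of the visit.
- Under Protocol 4.1.4.3 and SAP 4.2.2.1 each step is at most 5 mg/day HCe. The Day 1 result can lead only to a reduction, at about Week 2. Increases start from the Week 6 result.
- SAP 4.3.1.1: "Hormone assessments will be collected at all study visits except for Week 3 (safety laboratory assessments only".
- SAP 8.3.20.3 leaves stress doses out of the daily dose.

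On spread, SAP 6 gives two values: a planning calculation "assuming a standard deviation (SD) of 10.5 mg/day HCe", and later "Examination of group blinded data, provides a conservative SD estimate of 6.9 mg/day". It does not say which visit the 6.9 belongs to.

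**The concern.** Toeplitz, AR(1) and compound symmetry in their plain forms have a single variance parameter. Change in GC dose starts almost constrained and spreads as adjustments accumulate, so its variance should rise from Week 3 to Week 24. A common variance then averages the narrow early visits with the wide late one. It overstates the variance at Weeks 3 and 6 and understates it at Week 24, which SAP 12.3.3 names as the visit of principal interest.

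An understated Week 24 variance gives a standard error that is too small and a test that rejects too often. Under SAP 9.6 the secondary endpoints are tested only if the primary endpoint is met, so an inflated primary test also weakens the protection of that family.

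The clause could come into use. With no A4 drawn at Week 3 and no adjustment scheduled between Week 2 and the Week 6 visit, a subject who follows the algorithm has the same dose at both visits. If every subject did, the 5 x 5 covariance would have rank 4 and the unstructured fit would fail.

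**Working it through.** **The plan's own figures.** SAP 6 says "a sample size of N=40 subjects per group provides at least 90% power" for a "mean change in daily GC dose from baseline and placebo of 5 mg/day in HCe with a two-sided type I error of 0.05". With SD 6.9, the noncentrality is 5 / (6.9 x sqrt(2/40)) = 3.24 and power is 90.0%. The planning case (45 per group, 7.25 mg, SD 10.5) gives 7.25 / (10.5 x sqrt(2/45)) = 3.28 and 90.6%. Both reproduce.

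**Early variance.** Before the Week 6 visit an algorithm-adherent subject's change lies in [-5, 0] mg. A variable confined to a range of width 5 has variance at most 5²/4 = 6.25, so SD is at most 2.5 mg at Weeks 3 and 6.

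**Late variance.** By the Week 24 visit, adjustments from Day 1 and Weeks 6, 12 and 18 can have accumulated. If 6.9 is the Week 24 SD, the variance is 47.61 and the ratio is 47.61/6.25 = 7.6. The 6.9 comes from data pooled over arms. If it contains a true 5 mg difference, the within-arm variance is 47.61 - (5/2)² = 41.36 and the ratio is 6.6.

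**Compound symmetry, by hand.** With complete data and free visit-by-arm means, the fitted common variance is the mean of the five visit variances. Let r = Week 24 variance / mean variance. The standard error is multiplied by 1/sqrt(r), and the limiting error rate is 2 x [1 - Phi(1.96/sqrt(r))]. The variances at Weeks 12 and 18 are assumed:

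| Weeks 12 and 18 | Mean variance | r | SE too small by | Error rate |
|---|---|---|---|---|
| Already 47.61 | 31.07 | 1.53 | 19% | 11.3% |
| Linear in variance (20.04, 33.82) | 22.79 | 2.09 | 31% | 17.5% |
| SDs 4.2 and 5.6 (17.64, 31.36) | 21.82 | 2.18 | 32% | 18.5% |

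**Toeplitz and AR(1).** These were fitted in the limit by minimising log|V| + tr(V⁻¹S) against the assumed true covariance. Linear variance growth gives 15-17% for both. Variance already at its Week 24 level by Week 12 gives 12-13%.

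**Simulation.** Null trials with 45 per arm, complete data, a baseline covariate, a t reference and 3,000 runs per pattern:

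| Pattern | Toeplitz | AR(1) | Compound symmetry | Week 24's own variance |
|---|---|---|---|---|
| Linear variance growth | 14.3% | 14.4% | 15.8% | 4.7% |
| Plateau from Week 12 | 11.1% | 10.9% | 10.2% | 4.5% |

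The last column stands in for an unstructured or heterogeneous fit; the heterogeneous structures were not fitted one by one. Smaller runs (400 to 600 trials, margins of 3 to 4 points), some driven by the A4 rule itself, scattered between about 15% and 20%.

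**Sensitivity of the limiting rate, linear variance growth.** Week 24 SD 5 (ratio 25/6.25 = 4.0): 13-15%. SD 4 (ratio 16/6.25 = 2.6): 11-12%. Early SD raised to 3.5 to allow for overrides, compound symmetry: mean variance 26.39, r = 1.80, 14.5%. SD 10.5 (ratio 17.6): 17-20%.

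**The trigger.** In data generated strictly by the algorithm, the 5 x 5 covariance was singular in every run. With off-algorithm changes added at 5% of visits it was singular in none. In a separate check with 90 subjects, one subject whose Week 3 and Week 6 doses differed was enough for full rank in all 500 simulated matrices, with a Week 3 to Week 6 correlation of about 0.98. Three such subjects brought it to about 0.93.

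**The case against.** The strongest reply is that the clause may never be used. The first-choice model is right, it has only 15 covariance parameters, and it is fitted to completed datasets. Exact singularity needs equal Week 3 and Week 6 doses in every subject, and the documents give ordinary routes to a difference:

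- Protocol 7.1.5 provides for a GC increase after adrenal insufficiency from undertreatment, without tying it to an A4 visit.
- SAP 4.2.2.1 lets clinical judgement override the algorithm.
- Under SAP 4.3.1.2 a changed regimen must first be dispensed or prescribed and filled, and the Week 3 analysis window in SAP 8.4 opens on Day 8. A Week 3 record can therefore precede the Week 2 reduction.
- Protocol 4.1.4.1 accepts a 1 mg for 1 mg switch between prednisolone and prednisone although their HCe factors are 5 and 4.

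This stands. A reader might infer that the unstructured fit is bound to fail, or that the planned primary test has an error rate well above 5%. The documents support neither.

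A reader might also take a seven-fold rise in variance as guaranteed by the design. It is not. The 2.5 mg bound holds only for algorithm-adherent subjects, while the estimand is treatment policy in all randomized subjects. The 6.9 has no stated visit, is pooled over arms, and is called conservative by the SAP. Covariate adjustment may lower the relevant variance further. These points reduce the inflation without removing it, as the SD 4 and early SD 3.5 cases show.

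Finally, SAP 12.3.3 names no SAS covariance type, so heterogeneous versions could have been intended. The text does not say so, and the plain names ordinarily mean equal variance.

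**Conclusion.** The point holds as a conditional one. If the unstructured model fails and the listed structures are used as named, the Week 24 standard error is about 19-32% too small and the two-sided Type I error is roughly 10-18% instead of 5%. It is still about 11-12% if the Week 24 SD is only 4 mg. If the unstructured model converges there is no effect.

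The range assumes that most subjects follow the algorithm early on, that 6.9 mg (or about 6.4 within arm) describes Week 24, and that the chosen Week 12 and 18 variances and correlations are reasonable. None of the last three is given in the documents. The direction is firmer than the size: any marked growth in variance across visits makes an equal-variance fallback anti-conservative at Week 24. How likely the fallback is to be used cannot be worked out from the documents. Near-equal Week 3 and Week 6 doses make failure possible, no more.

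Week 24 is the principal comparison but not the only one. SAP 12.3.3 also extracts p-values at earlier visits, where a common variance would err the other way at Weeks 3 and 6. The clause should be corrected before unblinding, because replacing it afterwards would be post hoc.

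**What to change.** In SAP 12.3.3, replace the fallback list with heterogeneous Toeplitz, heterogeneous AR(1) and heterogeneous compound symmetry, in that order, then an ANCOVA of the Week 24 change if none converges. Each keeps a separate Week 24 variance. State the degrees-of-freedom method at the same time. The wording carries through to the imputed-data analyses in 12.3.3.1, which use the same model.

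The cost is SAP text, a covariance option in the program, and four more variance parameters in each fallback (five visit variances instead of one). Dropping Week 3 from the model is not required. It would change the visit set given in SAP 5.1.1, 12.3.3, 12.3.3.1 and 12.3.4 on the unproven premise that Week 3 always repeats the Week 6 dose.
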